8.1.7.2. Specimen Sampling and Handling

Blood samples for assessment of ILC2s will be collected and processed using the procedures in place at the investigational center [REDACTED]

8.1.8. Shipment and Analysis of Samples

Biomarker samples will be stored, shipped, and processed using the procedures in place at the investigational center [REDACTED]

8.2. Immunogenicity Testing

8.2.1. Blood Sampling and Handling

Blood samples (5 mL) for assessment of ADA response will be taken before and after dosing at the time points indicated in [Table 2](#). Unscheduled blood samples for anti-reslizumab antibody assessment will also be obtained from all patients experiencing a severe hypersensitivity reaction (eg, anaphylaxis).

Samples will be collected into labeled serum separator tubes and inverted slowly at least 5 times to thoroughly mix the blood with the clotting activation agent. Labels for samples should include study number, patient number, period, and nominal collection time. Blood samples will be left standing upright at room temperature (20°C to 25°C) to clot for approximately 30-60 minutes. Samples should then be centrifuged at a minimum of 1500 g for approximately 10 minutes at 4°C until clot and serum are well separated. Samples may be centrifuged at ambient temperature at 1500 g for 10 minutes as long as measures are taken as appropriate to prevent samples from heating significantly during centrifugation.

Separated serum will be transferred, in approximately equal portions, into 2 labeled cryovial tubes (primary aliquot A and back-up aliquot B) and stored in an ultralow freezer at $\leq -65^{\circ}\text{C}$ until shipped to a central or bioanalytical laboratory with temperature monitoring. Sample labels should include patient number, study number, collection date, and indication that it is an ADA sample aliquot (A or B). Storage at -15 to -20°C is acceptable for a period of up to 1 month if a $\leq -65^{\circ}\text{C}$ freezer is not available. The listed temperatures must be maintained. The actual times and dates of sampling will be recorded on the CRF.

8.2.2. Shipment and Analysis of Samples

Serum samples for immunogenicity assessment for all patients will be stored until shipped to the sponsor or its designee for analysis. Samples will be stored in an upright position at $\leq -65^{\circ}\text{C}$ until assayed. The central laboratory will be notified before the shipment of the samples and will be sent the shipping information when the samples are shipped. Set A samples will be transported with a temperature data logger and frozen with sufficient dry ice by next-day courier to the central laboratory.

Set B samples will either be sent to the same laboratory as that for set A on a later day by next-day courier, or be retained at the investigational center until the study is completed (unless shipment to another facility is requested by the sponsor).

Samples from reslizumab-treated patients will be analyzed using appropriate validated methods. Timing of the initiation of sample analysis will be determined by the Teva Pharmaceuticals bioanalytical department representative responsible for the bioanalysis. The bioanalytical team will not be blinded for this analysis.

Additional details regarding the collection, handling, and shipment of samples for measurement of anti-drug antibodies are provided in the investigator laboratory manual and its associated specimen collection summary.

9. STATISTICS

This section describes the statistical analysis as foreseen at the time of planning the study. Changes, additions, and further details about the analyses will be described in the statistical analysis plan. After finalization of the statistical analysis plan, any additional analyses or changes to analyses that may be required will be fully disclosed in the clinical study report (CSR).

9.1. Sample Size and Power Considerations

This study is exploratory in nature; therefore, no formal hypothesis testing is planned. Based on clinical and practical considerations, 5 healthy subjects and 10 eosinophilic asthma patients (5 patients treated with reslizumab, 5 patients treated with placebo) is considered adequate for:

1. a validation of the ability of PET/CT to differentiate patients with eosinophilic asthma from HCs
2. an evaluation of the effect of reslizumab versus placebo on inflammation of the lungs.

9.2. Analysis Sets

9.2.1. Intent-to-Treat Analysis Set

The intent-to-treat (ITT) analysis set will include all randomized patients. In this analysis set, treatment will be assigned according to the treatment to which patients were randomized, regardless of which treatment they actually received.

9.2.2. Safety Analysis Set

The safety analysis set will include all patients who receive at least 1 dose of study drug/placebo. In this analysis set, treatment will be assigned based on the treatment patients actually received, regardless of the treatment to which they were randomized.

The safety analysis set will be used for safety analyses of Part 2 of the study. In addition, safety analyses may present safety data from both Part 1 and Part 2 of the study as deemed necessary. For these analyses, the combined safety analysis set and enrolled analysis set (See Section 9.2.4) will be used.

9.2.3. Full Analysis Set

The full analysis set will include all patients in the ITT analysis set who receive at least 1 dose of study drug and have at least 1 postbaseline efficacy assessment.

9.2.4. Enrolled Analysis Set

The enrolled analysis set will include all patients enrolled to Part 1 of the study, including healthy subjects and patients with eosinophilic asthma.

9.3. Data Handling Conventions

For all variables, only the observed data from the patients will be used in the statistical analyses, ie, there is no plan to estimate missing data, unless otherwise specified.

9.3.1. Handling Withdrawals and Missing Data

Missing data will not be imputed, unless otherwise specified.

9.4. Study Population

Study population will be summarized for the ITT analysis set (see Section 9.2.1) as well as for the enrolled analysis set (see Section 9.2.4). Summaries will be presented by treatment group and for all patients.

9.4.1. Patient Disposition

Data from patients screened, patients screened but not randomized (and reason for not randomized), subjects/patients who are enrolled, patients who are randomized, patients randomized but not treated (and reason), patients in the ITT, safety, and full analysis sets, patients who complete the study, and patients who withdraw from the study will be summarized using descriptive statistics. Data from patients who withdraw from the study will also be summarized by reason for withdrawal using descriptive statistics.

9.4.2. Demographic and Baseline Characteristics

Patient and HC demographic and baseline characteristics, including medical history, prior medications and treatments, and ECG findings, will be summarized using descriptive statistics. For continuous variables, descriptive statistics (number [n], mean, standard deviation, median, minimum, and maximum) will be provided. For categorical variables, patient counts and percentages will be provided. Categories for missing data will be presented if necessary.

9.5. Efficacy Analysis

The efficacy endpoints for Part 2 of the study are discussed in Section 9.5.1 through Section 9.5.4.4.

9.5.1. Primary Endpoint

The primary efficacy endpoint is the change from baseline to week 4 in GLG (Δ GLG).

The supportive primary efficacy endpoint is the change from baseline to week 4 in LP SUVmean.

9.5.2. Secondary Endpoints

The secondary efficacy endpoints are:

- Change from baseline to weeks 2, 4, and 6 in blood eosinophil count
- Change from baseline to weeks 2, 4, and 6 in FEV₁
- Change from baseline to weeks 2, 4, and 6 in FeNO measurements

- Change from baseline to weeks 2, 4, and 6 in AQLQ scores

9.5.3. Exploratory Endpoints

The exploratory endpoints are:

- biological markers of inflammation and asthma:
 - IgE
 - DPP4
 - 25-hydroxy vitamin D
 - eotaxin-1, -2, and -3
 - TARC
 - MCP-1 and MCP-4
 - ILC2
- the global uptake of FDG in the lymph nodes and bone marrow as measured by the PET-CT imaging parameters indicated for the primary efficacy variable.
- sputum eosinophils for those patients that can produce sputum

9.5.4. Planned Method of Analysis

The ITT analysis set (see Section 9.2.1) will be used for summaries and the FAS will be used for all efficacy analyses. Summaries will be presented by treatment group.

9.5.4.1. Primary Efficacy Analysis

All imaging variables will be measured at 2 baseline visits and at weeks 2, 4, and 6 post-randomization.

Change in GLG from baseline to each of the postbaseline visits will be summarized using descriptive statistics (n, mean, standard deviation, median, minimum, and maximum) by treatment group. The difference in means between reslizumab and placebo will be summarized and reported.

No inferential statistics will be used for primary analysis and endpoint.

9.5.4.2. Supportive to Primary Efficacy Endpoint Analysis

The same methods as described in Section 9.5.4.1 will be used to describe the supportive endpoints to the primary endpoint.

9.5.4.3. Secondary Efficacy Analysis

The same methods as described in Section 9.5.4.1 will be used to analyze the secondary endpoints.

In addition, correlation between each of the secondary endpoints and change from baseline to week 4 in GLG will be calculated. Spearman's Rho correlation will be used for this analysis. No

inferential statistics will be used for secondary endpoints and analyses. Additional details about secondary endpoints analyses may be detailed in the statistical analysis plan.

9.5.4.4. Exploratory Efficacy Analysis

Analysis of the exploratory endpoints will be detailed in the statistical analysis plan (to be finalized and signed before unblinding).

9.6. Multiple Comparisons and Multiplicity

No adjustments will be made for the preplanned multiple comparisons/endpoints.

9.7. Safety Endpoints and Analysis

Safety analyses will be performed on the safety analysis set (Section 9.2.2). Safety analyses for the combined safety analysis set and enrolled analysis set, presenting safety data for Part 1 and Part 2 of the study may be presented as deemed necessary.

9.7.1. Safety Endpoints

Safety measures and time points are provided in [Table 2](#).

9.7.2. Safety Analysis

All adverse events will be coded using the Medical Dictionary for Regulatory Activities. Each patient will be counted only once in each preferred term or system organ class category for the analyses of safety. Summaries will be presented for all adverse events (overall and by severity). Patient listings of serious adverse events and adverse events leading to withdrawal will be presented.

Changes in laboratory and vital signs measurement data will be summarized descriptively.

The use of concomitant medications will be summarized by therapeutic class using descriptive statistics. Concomitant medications will include all medications taken while the patient is treated with study drug.

Newly occurring abnormalities in the physical examinations will be identified and listed.

For continuous variables, descriptive statistics (n, mean, standard deviation, median, minimum, and maximum) will be provided for actual values and changes from baseline to each time point. For categorical variables, patient counts and percentages will be provided. Descriptive summaries of serious adverse events, patient withdrawals due to adverse events, and potentially clinically significant abnormal values (clinical laboratory or vital signs) based on predefined criteria will be provided as well.

If any patient dies during the study, a listing of deaths will be provided and all relevant information will be discussed in the patient narrative included in the CSR.

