7.4. Clinical Laboratory Tests

All clinical laboratory test results outside of the reference range will be judged by the investigator as belonging to one of the following categories:

- abnormal and not clinically significant
- abnormal and clinically significant

A laboratory test result that has significantly worsened (according to investigator's medical judgment) from the baseline result will be recorded on the source documentation and should be repeated. An adverse investigational event includes a laboratory or diagnostic test abnormality (once confirmed by repeat testing) that results in the withdrawal of the patient from the study, the temporary or permanent cessation of treatment with study drug, or medical treatment or further diagnostic work-up. Any adverse clinical laboratory result should be monitored as described in Section 7.1.2. See Section 7.1.1 for a description of laboratory results that will be reported as adverse events.

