### 8.4. Clinical Laboratory Tests

Laboratory values and changes from baseline (Visit 4 or the last available value pre-dosing study medication) to endpoint (Visit 7) in laboratory test results (in standard international (SI) units)) will be presented, by treatment group and overall, using descriptive summary statistics (n, mean, SD, median, min, max), based on the safety analysis set (Part 2), for serum chemistry (Summary 15.3.2.1), and for serum hematology values and changes from baseline to each post-baseline visit (Summary 15.3.2.2). Urinalysis tests performed at Visits 4 and 7 will be summarized in Summary 15.3.2.3. Specific clinical laboratory tests performed at Screening (Visit 1) and at various visits throughout the study are presented in Table 2 below.

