**Table 2. Clinical Laboratory Tests**

Serum Chemistry	Hematology	Urinalysis
β human chorionic gonadotropin (HCG) a	hemoglobin	B-HCG a
calcium	hematocrit	protein
phosphate	red blood cell (RBC) count	glucose
sodium	RBC indices	ketones
potassium	platelet count	blood (hemoglobin)
chloride	white blood cell (WBC) count, and differential count and percentage	pH
creatinine	– absolute neutrophil count (ANC)	specific gravity
glucose	– polymorphonuclear leukocytes (neutrophils)	microscopic
blood urea nitrogen (BUN)	– lymphocytes	– bacteria
cholesterol (low density lipoprotein [LDL]/high density lipoprotein [HDL]/total) a	– eosinophils	– red blood cells (RBCs)
triglycerides a	– monocytes	– white blood cells (WBCs)
uric acid	– basophils	
alanine aminotransferase (ALT)	– atypical lymphocytes	
aspartate aminotransferase (AST)	– other (to include band granulocytes)	
lactate dehydrogenase (LDH)	international normalized ratio (INR)	
gamma-glutamyl transpeptidase (GGT)		
alkaline phosphatase		
bicarbonate or carbon dioxide		
creatinine phosphokinase		
total protein		
albumin		
total bilirubin		
direct bilirubin		
indirect bilirubin		

a Assessed at the screening visit only.

Shifts (below, within, and above the normal range) from baseline (Visit 4) to each post-baseline visit (hematology) and to endpoint (Visit 7, serum chemistry and urinalysis) will be summarized, by treatment group and overall based on the safety analysis set (Part 2), using patient counts (n) for each serum chemistry lab test (Summary 15.3.2.4), for each hematology lab test (Summary 15.3.2.5), and for each urinalysis lab test (Summary 15.3.2.6).

The incidence of post-baseline (including scheduled, unscheduled, and withdrawal visits) potentially clinically significant abnormal (PCS) abnormal values will be summarized for serum chemistry, hematology and urinalysis laboratory tests (Summaries 15.3.2.7, 15.3.2.8, and 15.3.2.9, respectively), using descriptive statistics (n, %) with the criteria for potentially clinically significant specified in Table 3 below.

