**Table 3. Criteria for Potentially Clinically Significant Laboratory Values**

Test	Criterion value*
Alanine aminotransferase (ALT)	≥ 3x ULN
Aspartate aminotransferase (AST)	≥ 3x ULN
Alkaline phosphatase	≥ 3x ULN
Gamma-glutamyl transpeptidase (GGT)	≥ 3x ULN
Lactate dehydrogenase (LDH)	≥ 3x ULN
Blood urea nitrogen (BUN)	≥ 10.71 mmol/L
Creatinine	≥ 177 mmol/L
Uric acid Men	≥ 625 mmol/L
Uric acid Women	≥ 506 mmol/L
Bilirubin (total)	≥ 34.2 mmol/L
Hematology	
Hematocrit Men	< 0.37 L/L
Hematocrit Women	< 0.32 L/L
Hemoglobin Men	≤ 115 g/L
Hemoglobin Women	≤ 95 g/L
Hemoglobin Adolescents (12 to 17 years)	≤ 100 g/L
White blood cell (WBC) counts	≤ 3 x 10  /L
	≥ 20 x 10  /L
Eosinophils	≥ 10%
Absolute neutrophil counts (ANC)	≤ 1 x 10  /L
Platelet counts	≤ 75 x 10  /L
	≥ 700 x 10  /L
Urinalysis	
Blood (HGB)	≥2 unit increase from baseline
Glucose	≥ 2 unit increase from baseline
Ketones	≥ 2 unit increase from baseline
Total protein	≥ 2 unit increase from baseline

\* ULN=upper limit of normal range.

For Creatine phosphokinase (CPK) parameter, no PSC will be calculated but the grading scale of the Guidance for Industry Toxicity Grading Scale for Healthy Adult and Adolescent Volunteers Enrolled in Preventive Vaccine Clinical Trials will be used to classify subjects in the four following grades (Summary 15.3.2.9) :

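### SAP Table 3 prints the limits for creatinine, uric acid and total bilirubin in mmol/L, 1000 times too high, so the summary of potentially clinically significant chemistry values would count none if the printed unit is applied

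*Protocol*

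**What the plan says.** Protocol 9.7.2 (Safety Analysis) commits to descriptive summaries of "potentially clinically significant abnormal values (clinical laboratory or vital signs) based on predefined criteria will be provided as well". The Protocol itself gives no numerical limits for the routine chemistry tests concerned here.

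SAP 8.4 fills the gap. It presents "laboratory test results (in standard international (SI) units", and after its Table 2 it says that the incidence of flagged post-baseline values will be summarised "with the criteria for potentially clinically significant specified in Table 3 below". The chemistry output is Summary 15.3.2.7.

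SAP Table 3 has ten chemistry rows:

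- Five (ALT, AST, alkaline phosphatase, GGT, LDH) are multiples of the upper limit of normal and carry no concentration unit.
- Five are concentrations, all printed in mmol/L: BUN 10.71, creatinine 177, uric acid 625 (men) and 506 (women), and total bilirubin 34.2.

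CPK is handled outside this table: "no PSC will be calculated but the grading scale of the Guidance for Industry Toxicity Grading Scale". Nothing else in either document restates or corrects the units of the five concentration rows. The SAP's introduction says that it prevails where the two documents differ.

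**The concern.** One unit is used for all five concentration limits, but the numbers do not belong to one unit. BUN makes sense in mmol/L. The other four make sense only in a unit 1000 times smaller.

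At stake is whether the chemistry table promised by the Protocol carries information. If data and limits are both put in mmol/L, the creatinine, uric acid and bilirubin counts are zero by construction in the reslizumab and placebo arms alike. A reader of that table could not tell such a zero from a true absence of abnormalities. The study has no Data Monitoring Committee and plans five patients per arm, so a single flagged patient is a visible part of the safety description.

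**Working it through.** **Inputs from the documents.** The five limits in mmol/L are from SAP Table 3. The unit system (SI) is from SAP 8.4.

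**Inputs assumed.** Molar masses are physical constants that the documents do not give: creatinine 113.12, uric acid 168.11, bilirubin 584.66 and urea nitrogen 28.014 g/mol. The documents give no reference ranges for these tests.

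**Formulas.** With M the molar mass:

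- from mmol/L: g/L = value × M / 1000, and mg/dL = value × M / 10
- from micromol/L: mg/dL = value × M / 10,000

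**Step 1: check row.** BUN: 10.71 × 28.014 / 10 = 30.0 mg/dL. This row is coherent in mmol/L as printed. In micromol/L it would be 0.03 mg/dL, so it must not be changed.

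**Step 2: the other four rows.** For creatinine, 177 × 113.12 / 10 = 2,002 mg/dL as printed, and 177 × 113.12 / 10,000 = 2.00 mg/dL if the unit is micromol/L. The rest follow in the same way.

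| Row | Number in Table 3 | As mmol/L (printed), g/L | As mmol/L (printed), mg/dL | As micromol/L, mg/dL |
|---|---|---|---|---|
| BUN | 10.71 | 0.30 | 30.0 | 0.03 |
| Creatinine | 177 | 20.02 | 2,002 | 2.00 |
| Uric acid, men | 625 | 105.07 | 10,507 | 10.51 |
| Uric acid, women | 506 | 85.06 | 8,506 | 8.51 |
| Total bilirubin | 34.2 | 20.00 | 2,000 | 2.00 |

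Table 3 gives a sense of scale from its own hematology rows. Its hemoglobin limits are 115 g/L (men) and 95 g/L (women). The printed uric acid limits, 105 and 85 g/L, would need almost as much uric acid in a litre of serum as those limits allow hemoglobin in a litre of blood. In micromol/L, all four limits fall on round mg/dL figures.

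**Step 3: effect on flagging.** Take a creatinine of 500 micromol/L as an illustration. This is 0.5 mmol/L. Against the printed limit it is 0.5 / 177 = 1/354 of the threshold and is not flagged. Against 177 micromol/L it is 500 / 177 = 2.8 times the threshold and is flagged.

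**Step 4: extent.** Four of ten chemistry rows are affected. Uric acid has two rows, so by analyte it is three of nine. The factor is exactly 1000 in each.

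**The case against.** **Abnormal values have other routes into the report.** A reader might infer that abnormal creatinine, uric acid or bilirubin could never be noticed in this trial. The documents do not support that. SAP 8.4 also plans "Shifts (below, within, and above the normal range) from baseline (Visit 4) to each post-baseline visit", with serum chemistry taken to visit 7 (Summary 15.3.2.4). It plans values and changes with minimum and maximum (Summary 15.3.2.1), and SAP 8.1 adds individual listings. Protocol 7.4 states: "All clinical laboratory test results outside of the reference range will be judged by the investigator". Protocol 7.1.1 makes clinically significant laboratory abnormalities adverse events. A zero count beside a raised maximum would invite questions. This objection stands and confines the point to one output.

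**The zero is conditional.** SAP 8.4 asks for SI units and does not name mmol/L for these tests. If the program compares the bare numbers with data held in micromol/L, the flags work. That also stands, but correct output would then depend on not following the written specification.

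**The print may be an artefact.** A micro sign read as the letter m would explain all four rows. The sign survives in SAP 2.1 (cells per microlitre), but that is running text. SAP Table 2 prints both a Greek beta and a Latin B for the same pregnancy hormone, so letter substitution in SAP tables is possible. On the other side, Table 3 carries an adolescent hemoglobin row in a study of ages 18 through 50, and Summary 15.3.2.9 is assigned to both urinalysis flags and CPK grades. Those suggest imperfect drafting. An artefact is unlikely but not excluded, so the source table must be checked.

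**The practical effect is small.** About ten patients are dosed, the Protocol schedules post-dose chemistry only at week 6 (visit 7), compromised renal function is an exclusion, and no efficacy analysis or decision uses Table 3. This stands and governs the severity.

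**Conclusion.** The point holds for SAP Table 3. The limits for creatinine, uric acid (both sexes) and total bilirubin are 1000 times too high in their printed unit; BUN is correct. Applied in that unit, Summary 15.3.2.7 would report zero for these tests in both arms regardless of the data.

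Protocol 9.7.2 contains no error. It makes the promise, and the SAP table fails to deliver it for three analytes. Nor do the documents show that a false zero is certain, since that depends on how the program handles units.

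The conclusion rests on standard molar masses, on the general knowledge that serum cannot hold 20 to 105 g/L of these substances, and on the printed table being a true copy of its source. Severity is low: it affects descriptive safety output only, and the abnormal values remain visible elsewhere.

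**What to change.** 1. Check the four rows against the source of SAP Table 3. If the source already shows micromol/L, nothing in the plan needs changing.
2. Otherwise change the unit to micromol/L for creatinine, uric acid (men), uric acid (women) and total bilirubin. Keep the numbers, and leave BUN in mmol/L.
3. Before database lock, confirm that the units in the program for Summary 15.3.2.7 match the units in which the laboratory data are held.

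The cost is four unit labels and one programming check. No new data or assessments are needed. SAP 2.5.2 already provides for SAP amendments to be approved before database lock.
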